6.7.2 Dietary Restrictions

6.7.2.1 Confinement Period

A standard diet will be designed by a dietician for the whole confinement period. For each meal, the caloric and fat content should be controlled in order to avoid a “high-fat” diet. A “high-fat” diet is defined as a diet which contains “approximately 50 percent of total caloric content of the meal [from fat] and is high in calories (approximately 800 to 1000 calories)” [37].

In order to avoid any effect on assessment of biomarkers of exposure, grilled or pan-fried meat, pre-cooked meats (e.g. tuna, ham, corned beef, and smoked meats), bacon and sausage will not be permitted. In addition, alcohol, broccoli, brussels sprouts, cauliflower, grapefruit and xanthine-containing foods and beverages (coffee, tea, chocolate, cocoa, mate, guarana, etc.) will not be allowed except when the subject will be asked to drink a cup of coffee for one of the assessment of CYP1A2).

Subjects will not be allowed to bring their own food (including sweets or chewing gum, etc.) or beverages to the investigational site. Meals will be served according to the agreed schedules. Additional light snacks, fruits (with the exception of grapefruits), and raw vegetables can be distributed to the subjects without restrictions at any time during confinement as long as they comply with the dietician’s standard diet. Consumption of non-carbonated water is allowed, however, should be carefully monitored. Consumption of quinine-containing drinks (e.g., tonic water) is not allowed during the study. The same menu and meal schedule will be administered uniformly for all subjects in both study arms.

In addition, for the purpose of the Ames test planned on Day -1 and Day 5, the menus served on Day -2 and Day 4 will be identical.

A fasting state has to be observed for at least 10 hours prior to blood drawings for:

- Safety laboratory on Day -1 and Day 6
- Clinical risk endpoints’ assessments in serum/plasma/blood on Day -1 and Day 6

Confidentiality Statement

Data and information contained in this document are considered to constitute trade secrets and confidential commercial information, and the legal protections provided to such trade secrets and confidential information are hereby claimed under the provisions of applicable law. No part of this document may be publicly disclosed without the written consent of Philip Morris Products S.A.

- Serum/plasma bio-banking samples for BoExp, clinical risk endpoints and other circulating proteins on Day -1 and Day 6
- Blood bio-banking for further transcriptomics, lipidomics and DNA methylation sequencing analyses on Day -1 and Day 6

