12.1.4 Definitions for Statistical Data Analysis

The following definitions (**Table 17**) for statistical analyses/presentations will be used:

Table 17: Definition of terms for the statistical analysis

Term	Definition
Baseline Value	The last valid assessment at the last available time point prior to first product use in the Exposure Period.

For 24-hour urine collections, the collection sample will be labelled by the day in which the collection started. As an example if the 24-hour urine sample is collected from Day 5 to Day 6, it will be analyzed and reported as the Day 5 sample.

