12.5.3.2 CYP2A6 Activity

If feasible, CYP2A6 will be analyzed in natural scale.

Descriptive statistics of the values and change from baseline on Day 6 and Day 90 Visit (Table 15.2.5.9) and supportive listings will be provided (Listing 15.3.5.6).

The analysis will compare the Day 6 and Day 90 Visit values between the CHTP 1.2 and CC arms. An ANCOVA model will be used with terms for baseline, sex, average daily CC consumption over the last 6 weeks as reported during admission and arm (Table 15.2.5.10).

The SAS code will be the same as described in Section “**12.5.1.1 Primary endpoints**”.

LS means for each arm along with the difference (CHTP 1.2 - CC) and 95% CI will be presented in the tables.

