12.5.3.3 Ames Mutagenicity Test

It is assumed that Ames Mutagenicity Test is log-normally distributed.

The 24 hour urine collection for the Ames mutagenicity test will be on Day -1, Day 5 and Day 90 Visit.

Descriptive statistics of the values and change from baseline of the YG1024+S9 mutagenicity will be provided (Table 15.2.5.11), along with listings (Listing 15.3.3.1).

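### Diet matching for the within-arm Ames change is incomplete, and the SAP plans no CHTP 1.2 versus CC estimate that would largely remove a menu effect shared by both arms

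*Protocol*

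**What the plan says.** On diet, Protocol 6.7.2.1 states that "for the purpose of the Ames test planned on Day -1 and Day 5, the menus served on Day -2 and Day 4 will be" the same. The sentence just before it reads: "The same menu and meal schedule will be administered uniformly for all subjects in both study arms". The section opens with: "A standard diet will be designed by a dietician for the whole confinement period". It excludes grilled, pan-fried, pre-cooked and smoked meats, bacon and sausage throughout confinement, but lets light snacks, fruit and raw vegetables be handed out freely within the dietician's standard diet.

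On sampling, SAP 12.5.3.3 states: "The 24 hour urine collection for the Ames mutagenicity test will be on Day -1, Day 5 and Day 90 Visit". SAP 12.1.4 fixes what those labels mean: "For 24-hour urine collections, the collection sample will be labelled by the day in which the collection started". Protocol Table A2 agrees, showing the Ames samples as Day -1 to Day 1, Day 5 to Day 6, and the first to second day of Visit 4.

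On analysis, SAP 12.5.3.3 assumes log-normality and then plans: "Descriptive statistics of the values and change from baseline of the YG1024+S9 mutagenicity will be provided". The table list in SAP 13.3.1 has one Ames table, the descriptive Table 15.2.5.11, and no analysis table. Protocol 3.3 places the Ames test under exploratory objective 1, which describes parameters in smokers who switch, compared with smokers who continue CC. For CYP2A6, under the same objective, SAP 12.5.3.2 says: "The analysis will compare the Day 6 and Day 90 Visit values between the CHTP 1.2 and CC arms".

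**The concern.** The protocol treats diet as something to control for the Ames test, since it prescribes menu matching for that purpose alone. The matching covers the day before each collection and leaves the collection day open. If the Day -1 and Day 5 menus differed in a way that alters urinary mutagenicity, the change from Day -1 to Day 5 would shift in both arms.

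The randomized CC arm, fed the same menus, is the natural protection. It works only if the arms are contrasted, and the SAP produces no contrast for this endpoint. A reader of the CHTP 1.2 change from baseline could take a menu effect for a product effect, or miss a product effect that the menu conceals, and would have no estimate or confidence interval for the comparison that the objective names.

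**Working it through.** The documents state no figure for the Ames test, so there is none to reproduce. The check has four steps.

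**1. Menu days against collection days** (Protocol 6.7.2.1 and Table A2; SAP 12.1.4 and 12.5.3.3)

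| Ames sample | Urine collected | Menu-matched day | Meals eaten during collection |
|---|---|---|---|
| Baseline | Day -1 to Day 1 | Day -2 | Day -1, no matching required |
| Day 5 | Day 5 to Day 6 | Day 4 | Day 5, no matching required |
| Day 90 Visit | first to second day of visit | none | no set menu (Protocol 6.7.2.2) |

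**2. How much of the dietary part the matched day could cover.** Assumptions: three equal meals at 08:00, 13:00 and 19:00; collection from 06:30; first-order excretion with half-life h; the same pattern every day. The meals then fall t = 1.5, 6.5 and 12.5 h into the collection. Let x be the mean of 2^(-(24 - t)/h) over the three meals and q = 2^(-24/h).

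- Share from collection-day meals: 1 - x
- Share from previous-day meals: x(1 - q)
- Share from earlier days: xq (the three shares sum to 1)

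Worked example at h = 9: the three terms are 0.177, 0.260 and 0.412, so x = 0.283 and q = 0.157. The shares are 0.717, 0.283 × 0.843 = 0.238, and 0.045.

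| h (hours) | Collection day | Previous day (matched) | Earlier days |
|---|---|---|---|
| 3 | 97% | 3% | 0% |
| 4 | 93% | 7% | 0% |
| 9 | 72% | 24% | 4% |
| 16 | 52% | 31% | 17% |
| 26 | 36% | 30% | 34% |
| 35 | 29% | 27% | 44% |

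The half-lives span values in Protocol Appendix D: 3 to 4 h for 3-hydroxybenzo[a]pyrene, 9 h for 2-NA, 26 h for 4-ABP, and up to 35 h for total 1-OHP. They belong to biomarkers of exposure; none is given for urinary mutagenicity. Under these assumptions the matched day supplies at most about a third of the dietary part at every half-life tried. The collection day dominates at short half-lives, and the two days are close to equal at long ones.

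**3. What a shared menu difference does to each summary.** All values are assumed. Let r be the product ratio at Day 5 and d the Day 5 to Day -1 menu multiplier, the same in both arms. The CC change is d - 1, the CHTP 1.2 change is rd - 1, and the ratio between arms is rd/d = r.

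| r | d | CC change | CHTP 1.2 change | CHTP 1.2:CC ratio |
|---|---|---|---|---|
| 0.5 | 0.8 | -20% | -60% | 0.50 |
| 0.5 | 1.0 | 0% | -50% | 0.50 |
| 0.5 | 1.25 | +25% | -37.5% | 0.50 |
| 1.0 | 0.8 | -20% | -20% | 1.00 |
| 1.0 | 1.25 | +25% | +25% | 1.00 |

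The same holds in an ANCOVA on the log scale. With E[log Day 5] = α + β log baseline + τ·arm, a menu shift common to all subjects at either time point changes α and leaves τ alone.

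If diet instead adds to the measurement, take a smoking contribution of 100, r = 0.5 and dietary amounts of 10 or 20:

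| Diet Day -1, Day 5 | CC change | CHTP 1.2 change | Difference of changes | Day 5 ratio |
|---|---|---|---|---|
| 10, 10 | 0 | -50 | -50 | 60/110 = 0.545 |
| 10, 20 | +10 | -40 | -50 | 70/120 = 0.583 |
| 20, 10 | -10 | -60 | -50 | 60/110 = 0.545 |

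Here the difference of changes is untouched. The ratio is pulled somewhat towards 1, and this happens even with matched menus. With no product effect the ratio is 1.00 in every case.

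**4. What the SAP plans under exploratory objective 1.** QSU-brief (12.5.3.1.1) and mCEQ (12.5.3.1.2) get repeated-measures models with an arm term. FTND (12.5.3.1.4) and CYP2A6 (12.5.3.2) get an ANCOVA with an arm term. ITUQ is tabulated in the CHTP 1.2 arm only, which its definition requires. The Ames test is measured in both arms, with a baseline, and gets no model.

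**The case against.** The strongest reply is that the design already handles diet. Both randomized arms eat the same menu, so any menu shift appears in the CC column too, and a reader who sets the columns side by side can spot it. This stands as an argument about bias: only a within-arm change read alone is exposed. It does not supply the missing estimate, because two descriptive columns give no ratio between arms and no interval for one.

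A second reply is that the plan owes nothing more. Objective 1 is worded as description, Protocol 12.6.3 promises only summaries for exploratory endpoints, and SAP 12.1.3 already gives geometric means with 95% CIs for log-normal data. This also stands: the missing model breaks no commitment. The case for adding it is that the objective is comparative and that four other endpoints under it receive a between-arm model.

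Third, a reader might infer that the protocol matched the wrong day. The documents do not support that. Food from the previous day is still being excreted during the collection, by up to about 31% of the dietary part in the table above, and at 26 to 35 h the two days contribute nearly equally. No text says that the Day -1 and Day 5 menus differ. The standard diet and the food exclusions apply on every confinement day, and both days share a 10-hour fast before blood draws and the same measured coffee (Protocol Tables 8 and 13). The matching is incomplete; it is not shown to be misplaced.

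Finally, menu matching would not touch the unrestricted snacks, fruit and raw vegetables. That is correct, and it limits what the menu change alone can achieve.

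**Conclusion.** The point holds in a limited form. Menu matching covers only the day before each confinement Ames collection, so diet control for the within-arm Day -1 to Day 5 change is incomplete. The between-arm contrast that would largely cancel a shared menu effect is not planned, although the objective is a comparison with continued CC use.

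A reader might go further and infer that the Ames result confounds diet with product. That does not follow for the comparison with CC, because both arms get the same menu. The cancellation is exact for a multiplicative effect. For an additive one, the Day 5 ratio moved only between 0.545 and 0.583 in the example.

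The size of any real bias cannot be derived from the documents. They give no half-life for urinary mutagenicity, no menus, and no estimate of the dietary part relative to smoking. The shares rest on assumed meal times and first-order excretion, and the effect sizes are illustrations. At the Day 90 Visit no menu is matched or common to the arms, so change from baseline is weaker there and the comparison with CC matters more; any balance in diet then comes from randomization. The endpoint is exploratory, and no primary or secondary analysis is affected. This is a minor improvement.

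**What to change.** In SAP 12.5.3.3, add the ANCOVA of SAP 12.5.1.1 on log-transformed Ames values at Day 5 and at the Day 90 Visit, with log baseline, sex, CC consumption and arm. Report the CHTP 1.2:CC geometric mean ratio with its 95% CI as the main Ames result, add an analysis table beside Table 15.2.5.11, and label within-arm change from baseline as supportive. If the database is already locked, run it as an additional analysis and identify it as such in the CSR, as SAP 13.3 provides.

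As a secondary change, Protocol 6.7.2.1 should make the Day -1 and Day 5 menus identical in addition to the Day -2 and Day 4 menus. If confinement is complete, the CSR should state whether the Day -1 and Day 5 menus were in fact the same.

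The cost is one extra exploratory model, with code already in the SAP, and one more matched pair of menu days. No new sample is needed.

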6.7.2.2 Ambulatory Period

The above dietary restrictions are not applicable for the ambulatory period.

One day prior to Visit 2, Visit 3, Visit 4, and during the visit on site, subjects will be asked by the site staff to refrain from consuming grapefruit or grapefruit-containing products, or quinine-containing drinks (e.g., tonic water). Alcohol, broccoli, brussels sprouts, cauliflower, chargrilled meat, xanthine-containing foods and beverages (e.g., coffee, tea, chocolate, cocoa, mate, guarana) will not be allowed on site during Visit 4.

A fasting state has to be observed for at least 10 hours prior to blood drawing for:

- Safety laboratory at Visit 2, Visit 3 and Visit 4
- Clinical risk endpoints' assessments in serum/plasma/blood at Visit 2, Visit 3 and Visit 4
- Serum/plasma bio-banking samples for BoExp, clinical risk endpoints and other circulating proteins, at Visit 4
- Blood bio-banking for transcriptomics, lipidomics and DNA methylation sequencing analyses at Visit 4

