4 INVESTIGATIONAL PLAN

4.1 Overall Study Design and Plan

This is a randomized, controlled, open-label, 2-arm, parallel group, single-center study with a stratified randomization by sex and average daily CC consumption over the last 6 weeks prior to Admission (smoking 10 to 19 CC/day vs. > 19 CC/day) (Figure 2).

This is an *ad libitum* smoking study. In general, smoking during confinement will be allowed between 06:30 AM and 11:00 PM.

During the confinement period, compliance to product/regimen allocation (exclusive use of CHTP 1.2 and CC in CHTP 1.2 and CC arms, respectively) will be ensured by strict distribution of each CHTP 1.2/CC on demand of the subject.

[figure not shown]

Figure 2 Study Design

Confidentiality Statement

Data and information contained in this document are considered to constitute trade secrets and confidential commercial information, and the legal protections provided to such trade secrets and confidential information are hereby claimed under the provisions of applicable law. No part of this document may be publicly disclosed without the written consent of Philip Morris Products S.A.

- The Screening Period (from Day -45 until Admission on Day -3):

The Screening Period covers 6 weeks prior to Admission to the site. A demonstration of CHTP 1.2 (without product use) will be done by the site collaborators during the Screening Visit. At the Screening Visit, spirometry needs to be done at least 1 hour after having stopped smoking. Use of any tobacco/nicotine containing product other than CC will not be allowed after the Screening Visit. At the end of the Screening Visit, subject will be instructed not to smoke in the morning prior to the admission to the site on the Admission Day.

- The Admission Day (from Admission on Day -3 until 06:29 AM of Day -2):

Subjects will be in a confinement setting for 9 days from Day -3 onwards.

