Data and information contained in this document are considered to constitute trade secrets and confidential commercial information, and the legal protections provided to such trade secrets and confidential information are hereby claimed under the provisions of applicable law. No part of this document may be publicly disclosed without the written consent of Philip Morris Products S.A.

Time	Blood Sample	Procedures	Additional Information
Start of Procedure		Day 90	
			The use of CHTP 1.2 in smokers allocated to CC is forbidden
During the visit		AE/SAE recording	
During the visit		Concomitant medications	
09:00 AM ± 30 min		Start of 24-hour urine sample collection for Day 90 (the first day of Visit 4)	The subject must empty his/her bladder and discard the urine prior to starting urine collection. The urine is collected for 24 hours ±1 hour
Prior to 11:30 AM		Intake of a cup of coffee made from 4.2 g (±10%) regular instant coffee; CAF content: 72 mg/2 g) with 150 ml ±10 ml water.	The time of intake of the cup of coffee must be recorded
After 11:30AM	√	CYP1A2 activity in plasma	6 hours ±15 minutes after intake of the cup of coffee
During the visit		CO breath test	Irrespective of the time of product use
During the visit	√	COHb in blood	Irrespective of the time of product use
During the visit	√	Plasma nicotine and cotinine sample	Cotinine will be measured in the same assay as nicotine. No additional blood samples required
8:00 PM - 11:00 PM		Prochaska Questionnaire (Intent to Quit)	
8:00 PM - 11:00 PM		QSU brief Questionnaire	
8:00 PM - 11:00 PM		MCEQ Questionnaire	
8:00 PM - 11:00 PM		FTND Questionnaire	
11:00 PM		End of use of IPs	

Confidentiality Statement

Data and information contained in this document are considered to constitute trade secrets and confidential commercial information, and the legal protections provided to such trade secrets and confidential information are hereby claimed under the provisions of applicable law. No part of this document may be publicly disclosed without the written consent of Philip Morris Products S.A.

Time	Blood Sample	Procedures	Additional Information
Start of Procedure		Day 90	
During the visit		Product use diary	To be completed by the subject. All IPs used including CHTPs 1.2, CC, and any tobacco/nicotine containing products have to be recorded.

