**Table 14: Assessment Windows**

Assessment	Nominal Time point(s)	Window
	Day 30 Visit, Day 60 Visit and Day 90 Visit	CC arm and prior to use of the first CHTP 1.2 in the CHTP 1.2 arm. Start at 09:00 ± 30 minutes (after bladder void) until 24-hours ±1 hour later.
Spirometry	Screening Day 6 and Day 90 Visit	spirometry without bronchodilator: at least 1 hour after having stopped smoking and prior to spirometry with bronchodilator spirometry with bronchodilator performed 15-30 minutes post administration of salbutamol spirometry will be performed prior to product use (CC or CHTP 1.2). spirometry post-bronchodilator performed 15-30 minutes post administration of salbutamol Day 6: 06:29 AM ± 1.5h Day 91: prior to 11:30 AM
CYP1A2 activity	Day -1, Day 5 and Day 90 Visit	6 hours after intake of cup of coffee ± 15 min
CYP2A6 activity	Day -3, Day 6 and Day 90 Visit	Prior to smoking / product use Day -3 and Day 90 Visit (Day 91): prior to 11:30 AM Day 6: 06:29 AM ± 1.5h
CO breath test	Day -2 to Day 5 Day -3, Day 30 Visit, Day 60 Visit and Day 90 Visit	in the evening around 08:00 PM ± 1.5 hour in conjunction (i.e., within 30 minutes) with COHb tests. First day of the respective visits; irrespective of time of product use
Assessment of Cough	Day -2 to 6 Day 30 Visit, Day 60 Visit and Day 90 Visit	To be done prior to product use but not later than 11:30 AM Second day of the respective visits; prior to 11:30 AM; irrespective of time of product use
Nicotine and cotinine in plasma	Day -1 to Day 6	Day -1 to Day 5: between 08:00 PM ± 1.5 hour. Day 6: between 06:29 AM ± 1.5h.

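### Coffee at home is not restricted or recorded before the Visit 4 CYP1A2 test, unlike before Day -1 and Day 5, so the Day 90 change from baseline is not measured under like conditions

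*Protocol*

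**What the plan says.** The SAP schedules the test at "Day -1, Day 5 and Day 90 Visit" (Table 14), with blood drawn 6 hours ± 15 minutes after the cup. Protocol 7.4.2.3 puts the cup at about 150 mg caffeine.

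The dietary conditions before the cup differ by visit:

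- **Confinement.** Protocol 4.1: "Subjects will be in a confinement setting for 9 days from Day -3 onwards". Protocol 6.7.2.1: "xanthine-containing foods and beverages (coffee, tea, chocolate, cocoa, mate, guarana, etc.) will not be allowed except when" for the CYP1A2 test cup itself.
- **Ambulatory period.** Protocol 6.7.2.2 opens: "The above dietary restrictions are not applicable for the ambulatory period". Its day-before request for Visits 2 to 4 names only grapefruit and quinine. For caffeine it says: "xanthine-containing foods and beverages (e.g., coffee, tea, chocolate, cocoa, mate, guarana) will not be allowed on site during Visit 4".
- **Day 90 timetable (Table 17).** Check-in is before 8:30 AM and the test cup before 11:30 AM. The time of the test cup is recorded.

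Secondary objective 8 is to describe the change in CYP1A2 activity in switchers compared with continuing smokers, at Day 5 and Visit 4. SAP 12.5.2.3 tabulates values and change from baseline, and compares the arms on Day 5 and at the Day 90 Visit by ANCOVA on the natural scale.

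**The concern.** At Day -1 and Day 5 both analytes come essentially from the test cup. At Visit 4 a habitual coffee drinker may arrive with caffeine and paraxanthine already circulating. The older dose carries proportionally more paraxanthine, so the measured ratio rises without any change in enzyme activity.

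At stake is the reading of CYP1A2 over time. Baseline and Day 5 values taken under controlled conditions are set beside Visit 4 values taken under uncontrolled ones. A real fall after switching could seem to have partly reversed by Day 90. Differences in coffee habit also add between-subject noise to the Day 90 comparison. No primary endpoint is involved.

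**Working it through.** **1. Caffeine-free time guaranteed before each test cup**

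- Day -1: the ban runs from admission on Day -3, so about two days.
- Day 5: the only caffeine permitted since admission is the Day -1 cup. There is no Day 0 (the nine confinement days run -3, -2, -1, 1 to 6), so that cup is five days earlier.
- Visit 4: from check-in to the cup, at most a few hours.

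**2. Does anything else close the gap?** No.

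- The 10-hour fast attaches to bloods drawn on Day 91 (Table 18). Table 17 requires no fast on Day 90.
- Protocol Table 3 lists caffeine as a CYP1A2 substrate, but under a rule on medications.
- The invalid-data rule in SAP 11.4 also concerns medication.
- No record of, or analysis rule for, coffee before the test cup was found.

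**3. The plan's own figure.** 4.2 g × 72 mg / 2 g = 151.2 mg (136 to 166 mg over ±10%), which agrees with about 150 mg.

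**4. Direction and size.** The documents give no caffeine or paraxanthine half-life and no home intake, so what follows is an assumption: linear kinetics, bolus input, 80% conversion (F = 0.8), caffeine half-life 3 to 6 h, paraxanthine half-life 3.1 to 5 h, home cup equal to the test cup.

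Per unit dose at time t, with k1 and k2 the elimination rates of caffeine and paraxanthine (ln 2 / half-life):

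- C(t) = exp(-k1·t)
- P(t) = F·k1/(k2 - k1) × [exp(-k1·t) - exp(-k2·t)]

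P/C for a single dose rises with t. With several doses, the ratio is the average of the single-dose ratios weighted by remaining caffeine. An older dose therefore always pulls it up.

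Example with half-lives 5.5 h and 4 h (k1 = 0.1260, k2 = 0.1733):

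- Test cup only: P(6)/C(6) = 0.2473/0.4695 = 0.53.
- One cup 2 h before: (0.2473 + 0.2451)/(0.4695 + 0.3649) = 0.59.
- Three cups 24, 19 and 14 h before: (0.2473 + 0.0369 + 0.0633 + 0.1049)/(0.4695 + 0.0228 + 0.0428 + 0.0804) = 0.4524/0.6155 = 0.73 to 0.74.

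| Home coffee before the test cup | Full-strength cups | Half-strength cups |
|---|---|---|
| One cup, 2 h before | +9 to +18% | +6 to +11% |
| Three cups the previous day | +15 to +59% | +8 to +34% |

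With wider half-lives (caffeine 2.5 to 10 h, paraxanthine 2 to 8 h, absorption phase added), three full-strength cups at 26, 20 and 16 h give +2 to +123%. The sign did not change in any case run.

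**5. Effect on each comparison.** Assume a caffeine half-life of 3.5 h while smoking and 5 h after switching, paraxanthine 4 h, and the same home coffee in both arms.

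| Day 90 condition | CC | CHTP 1.2 | CHTP/CC | Difference | CHTP fall from clean baseline (1.025) |
|---|---|---|---|---|---|
| Test cup only | 1.025 | 0.601 | 0.59 | -0.42 | 41% |
| One cup 2 h before | 1.176 | 0.676 | 0.57 | -0.50 | 34% |
| Three cups previous day | 1.343 | 0.830 | 0.62 | -0.51 | 19% |
| Both of these | 1.365 | 0.809 | 0.59 | -0.56 | 21% |

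The CC arm would show a spurious rise from baseline of 15% (1.176/1.025) or 31% (1.343/1.025) in the second and third rows.

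**6. What a run-in achieves.** In the 5.5 h / 4 h example, one cup 48 h earlier gives (0.2473 + 0.0022)/(0.4695 + 0.0011) = 0.530, or +0.6%. Over the wider half-life range the maximum is about 20%. Three cups with the last one 24 h before the test cup still leave about +3 to +33% over the narrower range, so one day helps but does not reproduce the baseline condition.

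**The case against.** The strongest defence is that objective 8 is comparative and the planned inference is between randomised arms at each visit. Both arms follow the same Visit 4 rule, so a shared coffee effect largely cancels. That stands in relative terms: CHTP/CC moves only from 0.59 to between 0.57 and 0.62. It does not cover the tabulated change from baseline, a reading of Day 5 against Day 90, the added variance, or the absolute difference on the natural scale that the SAP analyses.

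It is also fair that the size rests wholly on outside assumptions about half-lives and intake. The documents support a statement that the ratio may rise, by an unrecorded amount, in those who drank coffee. They do not show that it did.

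Lifting the confinement diet is explicit, and protocol 4.2 wants the ambulatory period to reflect real-world use. That explains free diet between visits. It does not explain leaving caffeine out of the day-before instruction while barring it on site.

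A reader might extend the point to the Ames test and total 1-OHP, since protocol 6.7.2.1 requires that "the menus served on Day -2 and Day 4 will be identical" and chargrilled meat is barred only on site at Visit 4. The documents give no size for a dietary effect on either, both arms share the rule, and the Ames analysis is descriptive only. That extension is not made here.

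**Conclusion.** The difference in pre-test conditions is in the text, and nothing in either document closes it. The upward direction follows from linear kinetics and held throughout the assumed range. The size is uncertain: about 9 to 18% for one full-strength cup 2 h before and 15 to 59% for three the previous day, less for weaker cups, and 2 to 123% for three cups on the wider half-lives. Confidence in the magnitude is moderate at best.

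Two distortions run in opposite directions and should not be confused. Change from baseline in the CHTP 1.2 arm looks smaller at Visit 4 than at Day 5. The untransformed Day 90 arm difference can look larger (-0.42 to between -0.50 and -0.56 in the illustration).

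A reader might conclude that the randomised Day 90 CYP1A2 comparison is invalid. The documents do not support that, because the rule is common to both arms and the relative contrast barely moves. This is a standardisation gap in one secondary objective, worth correcting because correction is cheap.

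**What to change.** - **Protocol 6.7.2.2:** reconcile with 6.7.2.1 by adding xanthine-containing foods and beverages to the existing day-before instruction for Visit 4, running to check-in.
- **Day 90 check-in (Table 17):** record caffeine intake over the previous 48 hours.
- **SAP 12.5.2.3:** repeat the Day 90 CYP1A2 comparison without flagged values, as a sensitivity analysis only, since exclusion selects on post-randomisation behaviour. Note that the one-day rule reduces carry-over without fully matching the baseline run-in.

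The cost is one sentence, one question and one extra analysis. The downside for subjects is one day of self-reported caffeine abstinence at home.

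This may come too late. Protocol version 5.0 (December 2016) says the 4-HNE samples have already been collected, and the SAP is dated January 2017, though neither states when the last Visit 4 took place. If sampling is complete, state the differing conditions in the clinical study report. Then rest CYP1A2 conclusions on Day 5 and on the relative between-arm contrast at Day 90, not on Day 90 change from baseline.
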